**Full Analysis Set (FAS):**

The FAS will include all patients who are randomized and received any amount of study drug.

**Safety Set (SAF):**

The Safety Analysis Set will include all patients that received any amount of study drug.

**Per Protocol Set (PPS):**

The PPS will include all patients in the FAS having received at least 2 full days of I.V. treatment and no protocol deviations listed in [Table 4.1](#) with relevant impact on efficacy data.

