
Study treatment
	
Treatment should start as soon as possible, Commercially Confidential Information after the time of onset of ICH symptoms, defined as the time the patient was last witnessed healthy.
 
The total treatment will last 14 days: 7 days of BAF312 i.v. infusion, titrated Commercially Confidential Information followed by 7 days of CCI BAF312 p.o. daily if the patient passes a swallowing safety evaluation. ICH patients who do not pass a swallowing safety evaluation per participating institutional standards will not be transitioned to the p.o. phase of treatment, and BAF312 must be discontinued after Day 7. These patients should continue to be followed for the remainder of the Assessment schedule; they should not be terminated from the study.

	Commercially Confidential Information
Pharmacokinetic assessments	Pharmacokinetic (PK) samples will be collected on Days 1, 8 and 14.
Efficacy/PD assessments	
CT imaging of the brain will be performed 24-48 hours after the initial diagnostic scan and on Days CCI 14.
 
Commercially Confidential Information
 
Modified Rankin Scale (mRS) and neurological examinations will be assessed on Days CCI 90.
 
Commercially Confidential Information

Key safety assessments	
 • Adverse event monitoring • ECGs • Vital signs • Physical and neurological examinations • Monitoring of laboratory markers in blood and urine
Other assessments	
 • N/A
Data analysis	
The primary analysis will be performed on the Per Protocol analysis set (PPS) defined as all patients having received at least the first infusion on Day1 and with no major protocol deviations impacting the analysis of efficacy.
 
The primary endpoint is reduction of absolute perihematoma edema (aPHE) volume based on CT imaging at Day 14 after ICH. The objective is to compare the mean aPHE between the BAF312 and placebo treatment groups.
 
Commercially Confidential Information

Key words	Stroke, intracerebral hemorrhage (ICH), BAF312, siponimod, sphingosine-1-phosphate (S1P) receptor, efficacy, safety, tolerability

1 Introduction

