11.1 Analysis sets

The Full Analysis Set will include all patients who are randomized and received at least one dose of study drug after randomization.

The Safety Analysis Set will include all patients that received at least one dose of study drug.

The Per Protocol Set (PPS) will include all patients in the full analysis set (FAS) having received at least the first infusion on Day 1 and no protocol deviations with relevant impact on efficacy data.

The PK Analysis Set will include all patients with at least one available valid (i.e., not flagged for exclusion) PK concentration measurement, who received any study drug and experienced no protocol deviations with relevant impact on PK data.

For all analysis sets, patients will be analyzed according to the study treatment(s) received.

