11.4.2 Statistical model, hypothesis, and method of analysis

It is expected that the distribution of aPHE is right-skewed (as it is a positive-valued measurement), so a log-transformation will be applied. The log-transformed absolute PHE volume on Day 14 will be analyzed using analysis of covariance (ANCOVA) model, with treatment as a classification factor and the baseline log-transformed aPHE as covariate. The mean difference (BAF312 vs. placebo) and its 90% CI will be calculated, and these estimates will be back-transformed to give a geometric mean ratio and 90% CI between BAF312 and placebo.

The primary analysis will be done on the PPS.

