**PK Analysis Set (PAS):**

The PAS will include all patients with at least one available valid (i.e., not flagged for exclusion) PK concentration measurement, who received any study drug and experienced no protocol deviations listed in table 4.1 with relevant impact on PK data.

For all analysis sets, patients will be analyzed per the study treatment(s) received.

All listings will use Randomized patients.

Frequency counts and percentages (using FAS as denominator) of patients in each of the above defined analysis sets will be summarized. In addition, listings of patients excluded from each of the analysis sets will be provided.

The analysis sets and protocol deviation are related to this study as follows:

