#### **5.1.1 Variables**

The primary efficacy variable is the aPHE volume measured on Day 14, which will be measured from the CT images by a central reading lab.

The primary analysis will be done on the PPS. A sensitivity analysis will be done on the FAS.

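### The exposure criterion for the primary analysis set differs between protocol (first infusion on Day 1) and SAP (2 full days of i.v. treatment), and both documents group the FAS by treatment received

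*SAP*

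**What the plan says.** **Which set is primary.** Protocol 11.4.2 states: "The primary analysis will be done on the PPS". SAP 5.1.1 agrees and adds a sensitivity analysis: "The primary analysis will be done on the PPS. A sensitivity analysis will be done on the FAS".

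**Exposure needed to enter that set.**
- Protocol summary, data analysis row: "all patients having received at least the first infusion on Day1 and with no major protocol deviations impacting the analysis of efficacy".
- Protocol 11.1: FAS patients "having received at least the first infusion on Day 1 and no protocol deviations with relevant impact on efficacy data".
- SAP 4.1: "all patients in the FAS having received at least 2 full days of I.V. treatment and no protocol deviations", with the deviations listed in Table 4-1.

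**How patients are grouped.** Protocol 11.1: "For all analysis sets, patients will be analyzed according to the study treatment(s) received". SAP 4.1: "For all analysis sets, patients will be analyzed per the study treatment(s) received". Both rules cover the FAS, which the SAP defines thus: "The FAS will include all patients who are randomized and received any amount of study drug".

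**Related text.** SAP 4.2 says that the analysis follows protocol section 11 as worked out in the SAP. Under protocol 7.2 and the footnote to the assessment schedule, patients who stop treatment before Day 14 without withdrawing consent still have the Day 14 CT. SAP Table 4-1 foresees a dispensing error in which a patient gets placebo throughout the i.v. phase and then oral BAF312, and excludes that patient from the PPS.

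**The concern.** The protocol gives the same exposure criterion twice and the SAP gives another. They cannot both define the primary population. Because SAP 4.2 presents the SAP as the detailed form of protocol section 11, an analyst would probably apply the 2-day rule. The protocol, which can be changed only by written amendment (13.1), would then describe a primary population that was not used.

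The choice is not purely administrative. The 2-day rule excludes patients for something that happens after randomisation and may be related to treatment. Protocol 6.6 places bradycardia and bradyarrhythmia with BAF312 typically in the first 48 hours of dosing. Protocol 7.2 lists hemodynamically significant bradycardia and third-degree AV block among the reasons for stopping, together with hematoma expansion or raised intracranial pressure that needs surgery. The first two could fall unequally between arms, and the others are tied to prognosis. These patients' Day 14 CTs would be collected and then left out of the primary analysis.

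The grouping rule is a separate and smaller matter. With the FAS also grouped by treatment received, the one visible sensitivity analysis does not preserve the randomised comparison if a dispensing error occurs. The mixed-pack patient whom the SAP foresees leaves the PPS but stays in the FAS with no clear arm.

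**Working it through.** **1. Reproduce the planned power.** Inputs from protocol 11.7: CV 90%, 30 evaluable patients per arm, 40% true reduction, one-sided alpha 0.05, stated power 80%. The analysis is on the log scale (protocol 11.4.2).
- Log SD = sqrt(ln(1 + 0.9²)) = sqrt(ln 1.81) = 0.770.
- Effect = −ln(0.60) = 0.511.
- SE = 0.770 × sqrt(1/30 + 1/30) = 0.199.
- Noncentral t with 58 df and noncentrality 0.511/0.199 = 2.57: power 81.4%. The stated 80% is reproduced.

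**2. Width of the gap between the criteria.** Protocol 3.1 has syringe changes every 6 hours, so 2 full days is 48/6 = 8 syringes. The protocol does not define the first infusion. If it means one syringe (assumption), the disputed stops lie between about 6 and 48 hours. If it means all of Day 1 (assumption), they lie between 24 and 48 hours.

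**3. Effect of exclusions on power.** The documents give no rate of stopping in this window, so the number excluded is varied, all from one arm:

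| Evaluable patients | SE | Power |
|---|---|---|
| 30 vs 30 | 0.199 | 81.4% |
| 29 vs 30 | 0.201 | 80.8% |
| 28 vs 30 | 0.202 | 80.2% |
| 27 vs 30 | 0.204 | 79.5% |

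**4. Effect of one exclusion on the estimate.** Removing one of 30 patients who lies 1 SD from the arm mean shifts that mean by 0.770/29 = 0.0266 on the log scale. The ratio is multiplied by exp(±0.0266), that is 0.974 or 1.027: about 2.7% in either direction, ignoring the baseline adjustment.

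**5. One patient traced through both documents.** Take a patient who gets the first day's infusions, stops permanently at 30 hours, has no listed deviation and has a Day 14 CT.
- Protocol PPS: included under either reading of first infusion.
- SAP PPS: excluded, because 30 hours is less than 48.
- FAS in both documents: included.

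The primary result depends on the document followed; the FAS result does not.

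**6. Grouping.** If every patient gets the assigned packs, grouping by treatment received and by randomised arm are the same. They differ only after a dispensing error. For the placebo-then-BAF312 patient of Table 4-1, treatment received is both, and neither document says which arm applies in the FAS.

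**The case against.** **The SAP may refine the protocol.** It postdates the protocol version it cites: its section 1.2 names a protocol of March 2019 and a DMC charter of August 2020. Section 4.2 supports reading it as the operative text. Completing the titration, which protocol 3.1 spreads over the first two days, is a plausible reason for a 2-day rule. This stands in part: it suggests which rule would be applied, but the visible SAP gives no reason and the two current definitions still differ. SAP section 9 and other parts are redacted, so an explanation there cannot be ruled out.

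**The effect is small.** This stands. Protocol 6.6 says that up-titration almost eliminates bradycardia, no early-stopping rate is given, the aim is a first efficacy estimate, and the FAS analysis keeps every disputed patient.

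**A reader might infer that the exposure criterion could be chosen after unblinding**, because SAP 4.1 issues a final version of the set assignment after database lock. The documents do not support this. Infusion duration can be judged blinded, and SAP 4.1 also requires a blinded review before lock to establish set assignment. The only visible criterion that needs the treatment code is the wrong-pack rule in Table 4-1.

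**A reader might also infer that the 2-day rule favours BAF312.** The documents do not show this: neither the number of early stops, nor their split by arm, nor their edema volumes can be derived from them.

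**Grouping by treatment received is no contradiction.** This stands: the documents agree with each other, the rule is usual for safety and PK sets, and the redacted supportive analyses may include one by randomised arm. The weakness is confined to the FAS. Extending randomised-arm grouping to the PPS could do harm: a patient given the wrong treatment in both phases is not caught by the visible wrong-pack exclusion and would count under a treatment never received.

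**Conclusion.** The concern holds as a mismatch of definitions. The primary population has two current exposure criteria, and patients who stop between them change sets. The plan should be corrected, but the evidence does not show an unworkable or biased primary analysis. With up to three exclusions from one arm, power stays between 81.4% and 79.5%; the ratio moves by about 2.7% per excluded patient at 1 SD. These figures rest on the protocol's CV of 90% and 40% reduction, a two-sample comparison without baseline adjustment, and an assumed number of exclusions. The mismatch itself rests on none of these assumptions.

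The FAS grouping is a secondary correction. It matters only if a dispensing error occurs, and it is subject to what the redacted supportive analyses contain.

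**What to change.** **(a) One PPS exposure criterion, before database lock.** State the same criterion in protocol and SAP, and define it: what counts as the first infusion (one syringe or all of Day 1), or how 2 full days are counted when infusions are interrupted. The protocol's criterion is the simpler choice, because it keeps observed Day 14 CTs and needs only a SAP amendment; if its definition is added to the protocol text too, that takes a protocol amendment. If the 2-day rule is kept, amend the protocol as well and give the reason.

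**(b) FAS by randomised arm.** Keep the Safety and PK sets by treatment received. Do not group the PPS by randomised arm unless every wrong-treatment patient is excluded from it. This changes protocol 11.1 and SAP 4.1, so it needs an amendment to each.

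Neither change needs new data.

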**PK Analysis Set (PAS):**

The PAS will include all patients with at least one available valid (i.e., not flagged for exclusion) PK concentration measurement, who received any study drug and experienced no protocol deviations listed in table 4.1 with relevant impact on PK data.

For all analysis sets, patients will be analyzed per the study treatment(s) received.

All listings will use Randomized patients.

Frequency counts and percentages (using FAS as denominator) of patients in each of the above defined analysis sets will be summarized. In addition, listings of patients excluded from each of the analysis sets will be provided.

The analysis sets and protocol deviation are related to this study as follows:

**Table 4-1 Protocol deviation and analysis sets**

---

**Text description of deviation**

---

**Subjects are excluded from Per protocol analysis set in case of these PDs:**

- Any protocol deviation from the category "Eligibility and Entry Criteria" which are all at least major (except if not considered by clinical team before the database lock).

---

**Text description of deviation**

---

- Any protocol deviation from the category “IP Compliance” corresponding to the major or critical deviation below:
  - Wrong medication pack dispensed resulting in injection of placebo during the whole i.v. phase followed by intake of BAF312 in the oral part.
- Any intake of prohibited medication corresponding to a protocol deviation category “Concomitant Medications Criteria” and taken during a certain period and likely to impact efficacy analysis.

---

**Subjects are excluded from PK analysis in case of same PDs as PPS except**

---

- Any intake of prohibited medication corresponding to a protocol deviation category “Concomitant Medications Criteria” and taken during a certain period and likely to impact PK analysis.
- 

If updates to this table are needed, an amendment to the SAP needs to be implemented prior to data base lock (DBL). The list of deviation will be review regularly to make sure the analysis set definition is as needed.

Prior to the locking of the database for final blind data reviews a blinded data review report will be written in order to establish analysis set assignment and to identify the potential reason(s) for exclusion of subjects from one or more of the analysis sets. As one of the criteria will request unblinded information a second version of the blind data review report will be created post database lock in order to indicate the final analysis set assignment as per IQVIA best practice.

## 4.2 Data analysis general information:

Data will be analyzed by IQVIA Biostatistics and Statistical Programming personnel according to the data analysis section 11 of the study protocol as detailed in this analysis plan. IQVIA standard operating procedures (SOPs) will be followed and some of the Novartis SOPs will be used, if deemed appropriate. Few analyses may be performed by NIBR Biostatistics group which is specified in advance in appropriate section.

SAS® version 9.4 (or later version if available at time of database lock) will be used for all analyses.

Data from all patients who signed informed consent will be used in the analysis; no center effect will be assessed as it is expected to have small sample size of enrollment at each individual centers. Each analysis will use all data in the database up to the analysis cut-off date, determined prior to database lock.

### General presentation of descriptive summaries and listings

The following summary statistics will be presented unless otherwise stated specifically. Qualitative/categorical data (e.g., gender, race) will be summarized by frequency counts and percentages. Percentages will be calculated using the number of patients in the relevant treatment arm or subgroup as the denominator.

Continuous data (e.g., age, body weight) will be summarized using appropriate descriptive statistics (i.e. mean, standard deviation (SD), lower quartile (q1), median, upper quartile (q3),

minimum, and maximum) by treatment arm. Based on the nature of the data, few analyses requires additional statistics such as geometric mean, geometric coefficient of variation (CV) and it will be specifically requested respective section.

In general, listings will be presented

- with country/center/subject identifier and age/sex/race as a mandatory column unless otherwise specified
- by treatment and patient

### 4.3 Subgroup of interest -

Result to swallowing test (success or fail) will be used as a covariate and as a subgroup for descriptive summary of mRS score.

Commercially Confidential Information

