1.1.3 Pharmacology of Sphingosine-1-Phosphate (S1P) Receptors

BAF312 (siponimod) acts as a selective modulator of two of the five sphingosine-1-phosphate (S1P) receptors: S1P₁ and S1P₅. T cells selectively require S1P₁ activation for emigration from the thymus, and both T- and B cells require this receptor for egress from peripheral lymphoid organs (Matloubian et al 2004, Brinkmann et al 2004).

Commercially Confidential Information

Two open label trials with another S1P-receptor modulator, fingolimod ([Fu et al 2014a](#), [Fu et al 2014b](#)), suggest an impact on edema formation and improved neurological outcome in ICH and ischemic stroke. However, limitations of the Fu et al. studies include lack of randomization, lack of placebo controls, and small sample sizes.

BAF312 is a second generation S1P receptor modulator that reduces peripheral lymphocyte counts approximately 4 – 6 hours (h) after the first dose. The half-life of BAF312 is approximately 30 h, which allows reversal of pharmacodynamic effects and recovery of the baseline lymphocyte counts within a week after treatment withdrawal. BAF312's mode of action is believed to include S1P₁-mediated prevention of effector lymphocyte recirculation from lymphatic tissue to sites of inflammation, such as the central nervous system (CNS). In addition, there may be direct beneficial effects in the CNS mediated by S1P₁ and/or S1P₅. Evidence from preclinical models suggests that BAF312 may target S1P₁ on astrocytes and/or S1P₅ on oligodendrocytes ([Choi et al 2011](#)).

We seek to evaluate whether reducing peripheral leukocyte count acutely after ICH would reduce PHE and decrease secondary injury after ICH, thereby improving outcomes in a prospective, randomized study with another S1P-receptor modulator, BAF312.

For more details, please see the Investigator's Brochure.

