3.1 Study design

This is a randomized, patient- and investigator-blinded, placebo-controlled, parallel group study of BAF312 on top of standard-of-care for ICH, consisting of 3 *epochs*: **Screening/Baseline, Treatment, and Follow-Up** (see [Figure 3-1](#)).

Screening/Baseline Epoch

The screening/baseline epoch lasts no longer than 24 hours from the time of onset of ICH, defined as the time the patient was last witnessed to be at their normal neurological baseline, and consists of:

- The initial diagnostic neuroimaging study (CT or MRI) to determine the cause of stroke
- Obtaining informed consent
- Determining the Glasgow Coma Scale (GCS, [Appendix 6](#)) score (see [Section 20](#)) on presentation
- Obtaining medical history, including current medications
- Hospital admission laboratory studies
- Electrocardiogram (ECG)
- Pregnancy test for premenopausal female patients
- Vital signs and physical examination, including neurological examination, and

Commercially Confidential Information

Please see [Assessment schedule](#) for details.

Treatment Epoch

Patients fulfilling all eligibility criteria must be randomly allocated to one of two treatment groups in a ratio of 1:1. The treatment should start as soon as possible, ^{Commercially Confidential Information} after the time of the ICH, defined as the time the patient was last witnessed to be healthy, defined as functioning at their normal, pre-event neurological baseline.

The total treatment lasts 14 days (see [Figure 3-1](#)):

- 7 days of i.v. BAF312 with titration to the final daily dose ^{Commercially Confidential Information}

Patients must be monitored with CV telemetry or continuous bedside monitoring for the first 48 hours of i.v. BAF312 treatment. During the 7 days of i.v. infusion treatment, all patients must undergo a swallowing safety evaluation per the treating hospital's institutional guidelines and practices.

- If the patients pass a swallowing safety evaluation, the 7-day i.v. phase is followed by 7 days of CCI BAF312 p.o. QD.
- Patients who do **not** successfully pass a swallowing safety evaluation **must not** be transitioned to the p.o. phase of treatment, and BAF312 **must** be discontinued after Day 7; but they should **not** be terminated from the study. These patients should continue to be followed for the remainder of the [Assessment schedule](#).

i.v. Dose Titration

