
Macular edema – The occurrence of macular edema with BAF312 in the present study is unlikely given the short treatment duration. However, the Investigator should be aware that patients with diabetes mellitus and previous uveitis might be at risk of developing macular edema. If the patient reports vision disturbances, they should be referred to an ophthalmologist for OCT measurement.

Radiation dose considerations from CT scans – Patients enrolled in this trial will have CCI non-contrast head CT scans- two as part of routine standard-of-care for ICH determination and follow-up (one at presentation/inclusion and another 24-48 hours later- corresponding to V1 and V2 in the [Assessment schedule](#)) and CCI follow-up study scans CCI at Days CCI 14 (V10). Scans from CCI Day 14 will be used for quantitative assessment of efficacy of BAF312 via determination of hemorrhage and edema volumes, as described elsewhere in this document. The effective radiation dose per scan is expected to be

approximately 2 mSv, amounting to a total of 8 mSv including the two standard-of-care scans (V1 and V2) ([McCollough et al 2015](#) and [Smith-Bindman et al 2009](#)). This is considered to be a minor to intermediate risk level corresponding to the benefit to the patient (category IIb based on [ICRP 62 1992](#)) and is balanced against the possible substantial societal benefit gained from the trial ([European Commission Radiation Protection 1998](#) and [ICRP 62 1992](#)). The radiation dose from CT scans will be in accordance with local clinical practice and regulations.

The investigators must regularly review the degree of burden and the risk threshold for the patients enrolled in this study.

There may be unknown risks with BAF312 which may be serious and unforeseen in the ICH patient population.

The treatment with BAF312 may benefit ICH patients. In a pilot study with another S1P₁ modulator (fingolimod), treated patients showed a reduction of neurologic impairment compared to placebo, regained a Glasgow Coma Scale score of 15 by Day 7; and had a NIHSS score reduction of 7.5 vs 0.5 in the placebo group ([Fu et al 2014a](#)).

Taking into account the nature of the known risks, the short duration of treatment, and the lack of alternative specific therapies for ICH, it is considered that the overall risk-benefit is favorable to study the therapeutic effect of BAF321 in ICH patients.

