6.5 Treating the subject

Once a patient meets all eligibility criteria and is randomized to a treatment arm, the treatment should start as soon as possible, CCI after the time of the ICH, defined as the time the patient was last witnessed to be healthy.

The total treatment lasts 14 days: 7 days of BAF312 with i.v. up-titration CCI (see [Figure 3-1](#)) followed by 7 days of CCI BAF312 p.o. once daily.

Commercially Confidential Information

As described in the accompanying Pharmacy Manual, syringe pump changes must occur every 6 hours, with a window of -15/+30 minutes.

During the i.v. up-titration period patients must be closely monitored. Special attention should be given to monitoring the HR and cardiac rhythm, with continuous CV telemetry in the Stroke Unit/Neurointensive Care Unit (Stroke/NICU) setting for at least the first 48 hours of the i.v. treatment phase. In case of symptomatic bradycardia or cardiac rhythm abnormalities (e.g. atrioventricular blocks or sinus pauses), the Investigator should follow the guidance given in

Section 6.6. Under those predefined conditions a dose may be postponed or skipped, but not more than 2 times in a row.

During the 7 days of i.v. infusion treatment, all patients must undergo a swallowing safety evaluation. Those ICH patients who do not successfully pass a swallowing safety evaluation per the treating hospital's institutional guidelines and practices will not be transitioned to the p.o. phase of treatment, and BAF312 must be discontinued after Day 7. Failure to pass a swallowing safety evaluation should be recorded in the source documentation, and patients who are unable to safely swallow oral medications should continue to be followed for the remainder of the [Assessment schedule](#); they should **not** be terminated from the study. The p.o. phase of treatment consists of five tablets to be taken whole, with or without food, in the morning.

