11.2 Subject demographics and other baseline characteristics

All data for background and demographic variables will be listed by treatment arm and patient. Summary statistics will be provided by treatment arm.

Patient demographics will include age, sex, race, ethnicity, height, weight and BMI.

Other baseline disease characteristics include relevant medical history, current relevant medication, blood pressure, GCS score, CCI historically estimated pre-stroke mRS score, hematoma volume, location of hematoma, time from first symptoms of ICH or last seen neurologically normal, and any other relevant information.

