#### **5.1.3.3 Graphical presentation of results**

Commercially Confidential Information

Percentage of ordinal mRS score at Day 90 will be displayed by treatment.

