### **Study drug exposure and compliance**

The total treatment lasts 14 days with two treatment phases (i.v. to p.o.) based on dose administration.

7 days of i.v. BAF312 with titration to the final daily dose Commercially Confidential Information

During the 7 days of i.v. infusion treatment, all patients must undergo a swallowing safety evaluation per the treating hospital's institutional guidelines and practices.

If the patients pass the swallowing safety evaluation, 7 days of CCI BAF312 p.o. QD.

Patients who do not successfully pass a swallowing safety evaluation must not be transitioned to the p.o. phase of treatment, and BAF312 must be discontinued after Day 7; but they should not be terminated from the study. These patients should continue to be followed as per the protocol assessment schedule.

Eligible patients who pass a swallowing safety evaluation will continue with 7-day p.o. phase of treatment with BAF312 CCI QD.

Information on the dose administration, amount, frequency (includes dose titration), reason for the dose change, start date and end date in eCRF pages collected for each of the treatment phase.

Overall study drug exposure, study drug exposure for individual phase (i.v. and p.o.) will be calculated as follows,

Overall drug exposure (days) =[date of last study treatment – date of first study treatment+1]

Study drug exposure in i.v. phase (days) =[date of last dose in i.v. phase– date of first dose in i.v. phase +1]

Study drug exposure in p.o. phase (days) =[date of last dose in p.o. phase– date of first dose in p.o. phase +1]

Overall drug exposure, study drug exposure in i.v. and p.o. phase will be summarized by treatment. In addition, frequency counts and percentages of patients who have dose decreases, increases in planned dose or dose interruptions, the corresponding reasons and average length of dose interruptions will be summarized separately for i.v. phase and p.o. phase.

Listing of drug administration will be presented with i.v. treatment phase on day 1-7 and another listing for p.o. phase on day 8-14.

During the 7 days of i.v. infusion treatment, all patients will undergo a swallowing safety evaluation. A listing will be provided for swallowing test by treatment.

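### SAP 4.3 names the swallowing-test result, obtained after randomisation and first dose, as a covariate for mRS; any mRS comparison adjusted for it can be biased if BAF312 affects early recovery

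*SAP*

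**What the plan says.** Under the subgroup heading, SAP 4.3 states: "Result to swallowing test (success or fail) will be used as a covariate and as a subgroup for descriptive summary of mRS score". The rest of that section is redacted.

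On timing, Protocol 3.1 says "During the 7 days of i.v. infusion treatment, all patients must undergo a swallowing safety evaluation"; Protocol 6.5 and SAP 8.2 agree. SAP 4.4 defines baseline as the last assessment at or before first dose, so a test scheduled within the infusion period does not qualify.

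The result also governs exposure. Under Protocol 6.5, patients who fail "will not be transitioned to the p.o. phase of treatment, and BAF312 must be discontinued after Day 7".

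The visible between-arm presentation of mRS is unadjusted. SAP 5.1.3.3 says "Percentage of ordinal mRS score at Day 90 will be displayed by treatment". The primary aPHE model in SAP 5.1.3 does not include the swallowing result.

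**The concern.** A covariate in a treatment comparison should be something treatment cannot have changed. The protocol gives reasons to think treatment might change this one. Protocol 1.1.3 asks whether lowering leukocyte counts early "would reduce PHE and decrease secondary injury after ICH, thereby improving outcomes". Protocol 3.7 cites a pilot of another S1P modulator in which treated patients "regained a Glasgow Coma Scale score of 15 by Day 7", the same window in which swallowing is tested.

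If BAF312 raises the pass rate, adjustment can mislead in two ways:

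- **Attenuation.** When benefit on mRS runs through early recovery, the swallowing result carries part of that benefit, and adjusting removes it.
- **False harm.** When the drug improves swallowing but not mRS, the BAF312 patients who pass include some with more severe strokes who would have failed on placebo. Comparing like result with like result then makes BAF312 look worse.

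Comparing arms within the pass or fail groups has the same problem.

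At stake is the reading of mRS. It is not a stated primary or secondary endpoint. However, Protocol 1.4 says the study is to judge whether the overall clinical profile warrants further development, and SAP 12.2 lists mRS with a direction of benefit. An adjusted contrast could disagree with the planned unadjusted display for reasons unrelated to drug benefit.

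**Working it through.** **The plan's own figures.** None is stated for mRS or swallowing. The one design figure is 80% power for aPHE with 30 per arm (Protocol 11.7). It reproduces: log-scale SD = sqrt(ln(1 + 0.9²)) = 0.770, effect = ln(0.6) = -0.511, one-sided α = 0.05, giving 29 per arm for 80% power and 81.4% at 30 per arm (noncentral t). The swallowing result does not enter this calculation.

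**Identity used.** For a linear model of mRS on treatment, with and without swallowing pass (1/0):

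unadjusted effect = adjusted effect + γ × (pass rate BAF312 − pass rate placebo),

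where γ is the mRS difference, pass minus fail, at fixed treatment. Passers do better, so γ is negative. With equal pass rates the two effects agree. With a higher pass rate on BAF312, the adjusted effect moves towards harm.

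**Simulation inputs (all assumed).** Placebo pass rate 50, 65 or 80%; correlation of early severity with swallowing 0.3, 0.5 or 0.7, and with mRS 0.5, 0.7 or 0.9; placebo mRS 0 to 6 distributed 3/10/15/17/28/12/15%; 1 million patients per arm.

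| Scenario | Unadjusted | Adjusted for swallowing |
|---|---|---|
| Drug lowers early severity by 0.3 SD, mid case (65%, 0.5, 0.7) | -0.332 | -0.284 (ratio 0.85) |
| Same, all 27 combinations | -0.24 to -0.43 | ratio 0.69 to 0.96 |
| Drug acts on mRS only, swallowing unchanged | -0.475 | -0.477 |
| Drug shifts swallowing by 0.3 SD, no mRS effect | 0.00 | +0.03 to +0.19 |
| No effect on either | 0.00 | 0.00 |

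In the 27 combinations the pass rate rises by 2 to 8 percentage points. For the mid case the identity can be followed by hand. The BAF312 pass rate is Φ(0.385 + 0.5 × 0.3) = Φ(0.535) = 0.704, a rise of 0.054. So γ = (-0.332 + 0.284)/0.054 = -0.89 mRS points.

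**Independent check with different assumptions.** Placebo pass rate 60%, both correlations 0.7:

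- Swallowing unchanged, true mRS effect -0.46: adjusted -0.46.
- No mRS effect, BAF312 pass rate 70, 75 or 80%: adjusted +0.12, +0.19 or +0.25. At 75% with both correlations 0.4: +0.06.
- BAF312 pass rate 75%, true mRS effect -0.46: adjusted -0.27, and -0.29 among passers.
- 30 per arm, no mRS effect: the two-sided 5% error rate becomes 7.5% at a 75% pass rate and 10.1% at 80%.

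These larger figures reflect larger assumed differences in pass rate, 10 to 20 points.

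**Scale against noise.** The assumed mRS distribution has mean 3.53 and variance 15.11 − 3.53² = 2.65, so SD 1.63. The standard error at 30 per arm is 1.63 × sqrt(2/30) = 0.42. The mid-case shift of 0.05 is about 0.1 standard errors; the largest false harm in the table, 0.19, is 0.19/0.42 = 0.45.

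**The case against.** The strongest objection is that the documents may not plan an adjusted mRS comparison at all. The sentence sits under a subgroup heading and ends with a reference to descriptive summary, which may govern both uses. If it governs only the subgroup, the outcome for the covariate is not named. The mRS model, if there is one, is redacted (Protocol 11.6; SAP 5.1.3.2, 7 and 12.1).

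This stands in part: the visible text does not prove that an adjusted test will be run, and no omission can be alleged. But in SAP 5.1.3 covariate means a model term. If only a table split was meant, the word is redundant and should go. No redacted text can turn the result into a pre-randomisation variable.

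The mechanism is also uncertain. No passage reports an effect of BAF312 on swallowing. The Day 7 evidence concerns fingolimod, from studies that Protocol 1.1.3 describes as small, non-randomised and without placebo control. Protocol 8.5.1 puts the edema plateau at Days 7 to 14, while swallowing may be tested earlier. All of this stands, and it is why the conclusion is conditional.

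Finally, the shift is small beside a standard error of 0.42. That also stands, and it limits the priority. It does not justify keeping an avoidable systematic error that needs only wording to remove.

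**Conclusion.** The concern holds, with medium confidence. Swallowing result is measured after first dose, could be affected by treatment, and partly determines treatment duration. Using it as a covariate in an mRS treatment comparison can bias that comparison whenever BAF312 changes the pass rate, and not otherwise.

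Under the main assumed inputs the size is 4% to 31% attenuation, or a false harm of +0.03 to +0.19 mRS points where the truth is zero. Neither can be derived from the documents, which give no pass rate, mRS distribution or correlation. The consequence is confined to any mRS contrast adjusted for swallowing and to arm comparisons within pass and fail groups. It should be corrected, but it does not threaten the primary result.

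**What to change.** In SAP 4.3:

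1. Delete the swallowing result as a covariate for any mRS treatment comparison.
2. State that any adjusted mRS comparison uses only variables fixed before randomisation and already collected, for example age, baseline GCS, and baseline hematoma volume or location. Protocol 11.2 already lists "hematoma volume, location of hematoma, time from first symptoms of ICH or last seen neurologically normal" among the baseline characteristics. Hematoma variables should come from the initial diagnostic scan, because Protocol 8.5.1 makes the scan 24 to 48 hours later the imaging baseline, and that scan may follow first dose.
3. Add pass/fail counts by arm, as a description of outcome and exposure, beside the output already planned in SAP 8.2: "A listing will be provided for swallowing test by treatment".
4. Label any mRS table by swallowing result as post-randomisation and descriptive, with no treatment contrast drawn within the pass or fail group.

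The cost is SAP wording and one count table. No new data are needed, and the clinical handling of the swallowing test is untouched.
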